4. STUDY DESIGN

4.1. General Design

This is a Phase 2, two-part, open-label in Part 1 and observer-blind, randomized, placebo-controlled in Part 2 study to evaluate the safety, tolerability, reactogenicity, and effectiveness of mRNA-1273.214 SARS-CoV-2 vaccine in infants aged 12 weeks to < 6 months. The study will be conducted at multiple sites in the US enrolling approximately 700 participants. Participants who withdraw or are withdrawn from the study will not be replaced.

The study will be conducted in 2 parts. Part 1 will consist of Arm 1 and Arm 2 that will enroll sequentially, ie, Arm 1 will begin enrollment and the periodic safety review will determine whether Arm 2 can begin enrollment. A total of 100 participants (50 participants in each arm) will be enrolled in Part 1 and will receive 5 µg of mRNA-1273.214 in Arm 1 and 10 µg of mRNA-1273.214 in Arm 2. While participants may be screened up to 1 month prior to dosing, they must be 12 weeks completed age at the time of receipt of first dose. Arm 1 will start with 2 doses of 5 µg (sentinel dosing) administered 8 weeks apart of up to 4 participants. An IST will review safety data after Dose 1 (1 week after Dose 1 of mRNA-1273.214) and provide a recommendation to further dose participants. Once safety and tolerability after Dose 1 have been reviewed by the IST, Arm 1 will continue enrollment for a total of 50 participants.

The IST will reconvene once 25 participants in Arm 1 reach Day 64 (1 week after Dose 2 of 5 µg administered 8 weeks apart). If no safety concerns are identified after IST review in Arm 1, Arm 2 will begin enrollment and participants will receive 2 doses of 10 µg of mRNA-1273.214 administered 8 weeks apart. Similar to Arm 1, safety and tolerability will be reviewed by the IST after 4 participants have received Dose 1 (1 week after Dose 1 of mRNA-1273.214), and again when 25 participants reach Day 64, and provide a recommendation for continuing dosing and enrollment at each review. Arm 2 will enroll a total of 50 participants. The immunogenicity and safety analysis will be conducted after all treated participants in both Arms 1 and 2 reach Day 85 (28 days from second dose). The results from Part 1 will determine the dose level for Part 2, which will be blinded and randomized.

Part 2 of the study will consist of 2 groups (Arm 3 and Arm 4). In Part 2, a total of approximately 600 participants will be randomly assigned to receive mRNA-1273.214 (Arm 3) or placebo (Arm 4) in a 1:1 ratio (n = 300 per arm). Part 2 will utilize the mRNA-1273.214 dose selected in Part 1. Study vaccine will be administered nonconcomitantly to routine pediatric vaccinations. Participants will be followed for approximately 12 months after completion of the primary series.

Protocol: mRNA-1273-P206, Original

All participants will participate in a Screening Period, Treatment Period, and Follow-up Period. The study schema is illustrated in Figure 1 and the SoA is provided in Table 1.

4.1.1. Study Periods

This study involves up to 10 scheduled visits in Part 1 and 8 scheduled visits in Part 2. In both Part 1 and Part 2, there will be up to 6 in-person visits (if screening and baseline are done separately) and 2 remote visits (Visit 3 and Visit 6; remote evaluation by means of telecommunication technology or phone call). Two additional clinic visits on Day 4 and Day 60 will be performed only in Part 1 (Table 1).

The study duration for each participant will be approximately 15 months, which includes 1 month for screening (Day –28 to Day –1), 2 months for dosing (on Day 1 and Day 57), and 12 months of follow-up after the second dose.

All scheduled study visits should be completed within the respective visit windows. If the participant is not able to attend a study site visit as a result of the COVID-19 pandemic (self-quarantine or disruption of study site activities following business continuity plans and/or local government mandates for "stay at home" or "shelter in place"), a remote evaluation via a telemedicine visit or call should be conducted in place of the study site visit (except for dosing visits and visits that require a blood draw). The remote evaluation should encompass all scheduled visit assessments that can be completed remotely, such as assessment for AEs and concomitant medications (eg, as defined in scheduled safety telephone calls). Home visits will be permitted for all nondosing visits, with the exception of screening, if a participant cannot visit the study site as a result of the COVID-19 pandemic. Home visits must be permitted by the study site IRB and the participant's parent(s)/LAR(s) via informed consent and have prior approval from the Sponsor (or its designee).

This study will be conducted in compliance with the protocol, GCP, and all applicable regulatory requirements (Section 11.1.1).

4.1.1.1. Screening Period

Participants will undergo screening assessments to determine study eligibility. Screening assessments (Table 1) must be completed after the participant's parent(s)/LAR(s) signs the ICF. The investigator will review study entry criteria to determine participant eligibility during the screening period.

Screening Visit and Day 1 may be combined on the same day. Additionally, the Screening Visit may be performed over multiple visits if performed within the 28-day screening window (Table 1).

Protocol: mRNA-1273-P206, Original

Eligible participants will enter the Treatment Period.

4.1.1.2. Treatment and Follow-up Period

In both Parts 1 and 2, on Day 1, after the completion of the scheduled assessments (Table 1), participants will be administered a single IM dose of the IP mRNA-1273.214 (at the applicable dose based on study part and arm) or placebo. Placebo will be administered only to those who are randomized to the placebo arm in Part 2 of the study. The procedures for IP administration will be detailed in the mRNA-1273-P206 Pharmacy Manual.

Participants will be closely monitored for safety and will remain at the study site for observation for at least 60 minutes after dosing in Part 1 and 30 minutes after dosing in Part 2. On Day 57, the second dose of IP will be administered. If the visit for the second dose (Day 57) is disrupted and cannot be completed at Day 57 (-14/+7 days) as a result of the COVID-19 pandemic (self-quarantine or disruption of study site activities following business continuity plans and/or local government mandates for "stay at home" or "shelter in place") or due to extenuating circumstances (to be evaluated by the Sponsor on a case-by-case basis), the visit window may be extended to Day 57 + 14 days. When the extended visit window is used, the remaining study visits should be rescheduled to follow the intervisit interval from the actual date of the second dose.

Participants will be followed for 12 months after the second dose of IP. To test for the presence of SARS-CoV-2 by RT-PCR, nasal swab samples will be collected on each day of injection prior to dosing (Day 1 and Day 57), and on Day 85 (28 days after Dose 2), Day 237 (6 months after Dose 2), and Day 422 (12 months after Dose 2) according to the SoA (Table 1).

During the course of the study, participants who meet prespecified disease criteria that suggest possible SARS-CoV-2 infection will be asked to contact the study site to arrange for a prompt, thorough, and careful assessment, including a nasal swab sample to be tested for the presence of SARS-CoV-2 by RT-PCR. Confirmed, symptomatic cases of SARS-CoV-2 infection will be captured as MAAEs and, if severe, reported in an expedited time frame to the Sponsor (Section 8.11.4).

All participants will be monitored for safety and reactogenicity. All participants in the study will provide blood specimens for immunogenicity assessments on Day 1 (prior to the first dose), Day 85 (28 days after Dose 2), Day 237 (6 months after Dose 2), and Day 422 (12 months after Dose 2).

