Cases are defined as participants meeting clinical criteria based both on symptoms for COVID-19 and on RT-PCR detection of SARS-CoV-2 from samples collected within 72 hours of the study participant reporting symptoms meeting the definition of COVID-19. Participants who are hospitalized for COVID-19 without the opportunity for a clinic or home visit will also be considered cases, assuming that the symptomology criteria for COVID-19 are met and a respiratory sample is positive for SARS-CoV-2 by RT-PCR at a certified laboratory.

Investigators are encouraged to try to obtain a respiratory sample during the course of hospitalization or immediately after hospital discharge as an unscheduled visit for submission to the study central laboratory, if feasible. The investigator should determine if the criteria for severe COVID-19 have been met.

Severe COVID-19 is defined in Section 8.9.2.

All clinical findings will be recorded in the eCRF. All confirmed cases of symptomatic COVID-19 will be captured as MAAEs if an illness visit was conducted at the site or if they were evaluated by a healthcare provider, along with relevant concomitant medications and details about severity, seriousness, and outcome, and will be collected throughout the study period (Section 8.11.4).

Protocol: mRNA-1273-P206, Original

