8.11.4. Medically Attended Adverse Events

An MAAE is an AE that leads to an unscheduled visit to an HCP. This would include visits to a study site for unscheduled assessments (eg, abnormal laboratory test result follow-up, COVID-19 [Section 8.9.2]) and visits to HCPs external to the study site (eg, urgent care, primary care physician). Investigators will review unsolicited AEs for the occurrence of any MAAE. Unsolicited AEs will be captured on the AE page of the eCRF.

All confirmed symptomatic COVID-19 cases (Section 8.9.2) will be recorded as MAAEs. Any severe COVID-19 cases will be reported to the Sponsor or designee immediately and in all circumstances within 24 hours, using the SAE Mailbox, the SAE Hotline, or the SAE Fax line (Section 8.11.10). The investigator will submit any updated COVID-19 case data to the Sponsor within 24 hours of it being available.

All suspected cases of anaphylaxis associated with study drug administration should be recorded as MAAEs and reported as an AESI and SAE, based on criteria for a medically important event, unless the event meets other serious criteria. As an SAE, the event should be reported to the Sponsor or designee immediately and in all circumstances within 24 hours as per Section 8.11.10. The investigator will submit any updated anaphylaxis case data to the Sponsor within 24 hours of it being available. For reporting purposes, a participant who displays signs/symptoms consistent with anaphylaxis as described below should be reported as a potential case of anaphylaxis. This is provided as general guidance for investigators and is based on the Brighton Collaboration case definition (Rüggeberg et al 2007).

Anaphylaxis is an acute hypersensitivity reaction with multi-organ-system involvement that can present as, or rapidly progress to, a severe life-threatening reaction. It may occur following exposure to allergens from a variety of sources.

Anaphylaxis is a clinical syndrome characterized by:

- Sudden onset AND
- Rapid progression of signs and symptoms AND
- Involves 2 or more organ systems, as follows:
 - Skin/mucosal: urticaria (hives), generalized erythema, angioedema, generalized pruritus with skin rash, generalized prickle sensation, red and itchy eyes

Protocol: mRNA-1273-P206, Original

 Cardiovascular: measured hypotension, clinical diagnosis of uncompensated shock, loss of consciousness or decreased level of consciousness, evidence of reduced peripheral circulation

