3.1. Primary Endpoints

The primary safety objective for Part 1 and Part 2 will be evaluated by the following safety endpoints:

- Solicited local and systemic adverse reactions (ARs) through 7 days after each injection
- Unsolicited adverse events (AEs) through 28 days after each injection
- Medically attended AEs (MAAEs) throughout the entire study period
- Serious AEs (SAEs) throughout the entire study period
- AEs of special interest (AESIs) throughout the entire study period
- AEs leading to discontinuation from study participation postdose throughout the entire study period

The primary immunogenicity objective to infer effectiveness of the mRNA-1273.214 vaccine for Part 2 will be evaluated by:

- Co-primary Endpoint: geometric mean (GM) value of antibodies (Ab) against SARS-CoV-2 VOC (Omicron) at 28 days after the second dose of mRNA-1273.214 compared with that of the adult participants at Day 57 (28 days after the second dose) in Study mRNA-1273-P301 dosed with mRNA-1273 (100 μg, 2 doses 28 days apart) primary series
- Co-primary Endpoint: seroresponse rate (SRR) against SARS-CoV-2 VOC (Omicron) at 28 days after the second dose of mRNA-1273.214 compared with that of the adult participants at Day 57 (28 days after the second dose) in Study

mRNA-1273-P301 dosed with mRNA-1273 (100 μg , 2 doses 28 days apart) primary series

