6.3.1. Adverse Events

A treatment-emergent AE (TEAE) is defined as any event occurring during the study not before exposure to study vaccine or any event already present that worsens after exposure to study vaccine. [Note: worsening of a pre-existing condition after vaccination will be reported as a new AE.]

Adverse events will also be evaluated by the investigator for the coexistence of MAAE which is defined as an AE that leads to an unscheduled visit to a healthcare practitioner.

Unsolicited AEs will be coded by PT and SOC using MedDRA and summarized by vaccination group, and stage (up to 28 days after any vaccination for Part 1 and Part 2 separately and overall stage (throughout the study); see Section 6.1 for definitions of vaccination group and stage).

All summary tables (except for the overall summary of AEs) for unsolicited AEs will be presented by SOC and PT for AEs with counts of subjects included. SOC will be displayed in internationally agreed order. PT will be displayed in descending order of frequency of total mRNA-1273.214 group with all dose level combined in Part 1 and mRNA-1273.214 group in Part 2 and then alphabetically within SOC. When summarizing the number and percentage of subjects with an event, subjects with multiple occurrences of the same AE or a continuing AE will be counted once. Subjects will be presented according to the highest severity (the strongest relationship) in the summaries by severity, if subjects reported multiple events under the same SOC and/or PT.

Percentages will be based upon the number of subjects in the Safety Set within each vaccination group for Part 1 and Part 2 separately.

6.3.1.1.Incidence of Adverse Events

An overall summary of unsolicited AEs including the number and percentage of subjects who experience the following will be presented:

- Any unsolicited AEs
- Any serious unsolicited AEs
- Any fatal unsolicited AEs
- Any unsolicited medically-attended AEs
- Any unsolicited AEs leading to discontinuation from study vaccine
- Any unsolicited AEs leading to discontinuation from participation in the study
- Any unsolicited Severe AEs
- Any unsolicited Non-serious AEs
- Any unsolicited Non-serious and Severe AEs
- Any AESI of multisystem inflammatory syndrome in children (MIS-C)
- Any AESI of myocarditis and/or pericarditis
- Any AESI other than MIS-C and myocarditis and/or pericarditis

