The table will also include number and percentage of subjects with unsolicited AEs that are treatment-related in each of the above categories.

In addition, separate listings containing individual subject adverse event data for unsolicited AEs, unsolicited AEs leading to discontinuation from study vaccine, unsolicited AEs leading to discontinuation from participation in the study, severe AEs, serious AEs, unsolicited medically-attended AEs, AESI other than MIS-C and myocarditis and/or pericarditis, AESI of MIS-C and AESI of myocarditis and/or pericarditis will be provided separately.

6.3.1.2.AEs by System Organ Class and Preferred Term

The following summary tables of AEs will be provided by SOC and PT using frequency counts and percentages (i.e., number and percentage of subjects with an event):

- All unsolicited AEs
- All unsolicited AEs that are treatment-related
- All serious unsolicited AEs
- All serious unsolicited AEs that are treatment-related
- All unsolicited AEs leading to discontinuation from study vaccine
- All unsolicited AEs leading to discontinuation from participation in the study
- All unsolicited AEs leading to discontinuation from participation in the study that are treatment-related
- All unsolicited Severe AEs
- All unsolicited Severe AEs that are treatment-related
- All unsolicited medically-attended AEs
- All unsolicited medically-attended AEs that are treatment-related
- All AESI of MIS-C
- All AESI of myocarditis and/or pericarditis
- All AESI other than MIS-C and myocarditis and/or pericarditis
- All unsolicited AEs with occurrence in ≥1% of participants in any treatment group based on PT

Additionally, the following summary tables of AEs will be provided by PT using frequency counts and percentages:

- All unsolicited AEs
- All unsolicited AEs, presented by Standardized MedDRA Queries (SMQ) and PT.

6.3.1.3.AEs by System Organ Class, Preferred Term and Severity

The following summary table of AEs will be provided by SOC, PT, and maximum severity (mild < moderate < severe) using frequency counts and percentages:

All unsolicited AEs (Any vs. Related)

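### In Part 2, confirmed COVID-19 is counted among medically attended (and sometimes serious) AEs, so vaccine protection can dilute an excess of other events in the whole-study aggregate rows

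*Protocol*

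**What the plan says.** Protocol 4.1.1.2 states "Confirmed, symptomatic cases of SARS-CoV-2 infection will be captured as MAAEs". Protocol 8.11.4 is equally unconditional: "All confirmed symptomatic COVID-19 cases (Section 8.9.2) will be recorded as MAAEs". Under Protocol 8.9.2, a case needs one listed symptom, which may be a runny nose, plus a positive RT-PCR. Under Protocol 8.11.2, an overnight admission makes an event serious. Asymptomatic infection is not an MAAE under these rules.

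Other sections attach a condition to the recording. Protocol 8.9.3 says "COVID-19 will be captured as MAAEs if an illness visit was conducted at the site or if they were evaluated by a healthcare provider". Section 8.9.3.1 refers to assessment at a site visit or by another healthcare provider. Section 8.9.4 mentions only a site visit.

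SAP 3.1 lists "Medically attended AEs (MAAEs) throughout the entire study period" as a primary safety endpoint and does the same for SAEs. The overall table in SAP 6.3.1.1 has the row "Any unsolicited medically-attended AEs", with rows for serious and severe events. It also gives the "number and percentage of subjects with unsolicited AEs that are treatment-related in each of the above categories". For SAP 6.3.1.2 the plan is: "The following summary tables of AEs will be provided by SOC and PT using frequency counts and percentages". Listings are planned too. None of these summaries excludes COVID-19.

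COVID-19 incidence by vaccination group is reported separately in Part 2, as an exploratory analysis (Protocol 9.5.3, SAP 6.5).

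**The concern.** Protocol 4.2 justifies the placebo arm as necessary for assessing safety. The illness that the vaccine is meant to prevent nevertheless sits inside two primary harm endpoints. If the vaccine protects, the vaccine arm has fewer COVID-19 MAAEs and SAEs, and the aggregate row shows harm net of benefit. Similar percentages in the two arms would then not show that other medically attended events are similar.

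The COVID-19 share could matter. The Protocol expects the virus to be circulating, the case definition is broad, and active surveillance prompts illness visits that themselves count as medical attendance. Mild illness therefore enters the count partly because of the protocol's own procedures.

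**Working it through.** **The plan's own safety figure.** Protocol 9.3 claims at least 90% probability of seeing one or more participants with an AE at a true rate of 1% among about 300 vaccinees. 1 − 0.99^300 = 95.1%, so the claim holds. It does not bear on this point. The documents give no MAAE rate, attack rate or level of protection.

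**Inputs.** About 300 per arm (Protocol 9.3; SAP 4.4). Everything else is assumed: *b*, the proportion of placebo infants with a non-COVID MAAE; *x*, the true excess of such infants on vaccine; *c*, the placebo COVID-19 attack rate; *VE*, the proportional reduction on vaccine; and independence of COVID-19 and other MAAEs.

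**Formula.**
- Placebo, any MAAE: 1 − (1 − b)(1 − c)
- Vaccine, any MAAE: 1 − (1 − b − x)(1 − c(1 − VE))
- Difference: x(1 − c(1 − VE)) − (1 − b)·c·VE

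**Illustration with b = 40% and x = 8 points.**

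| Attack rate, reduction | Placebo | Vaccine | Difference shown |
|---|---|---|---|
| 3%, 50% (28-day period) | 41.8% | 48.8% | +7.0 |
| 10%, 30% (whole study) | 46.0% | 51.6% | +5.6 |
| 20%, 50% (whole study) | 52.0% | 53.2% | +1.2 |

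The 3% comes from assuming 20% over about 422 days at constant risk. The two 28-day post-dose periods cover 56 days, and 1 − 0.8^(56/422) = 2.9%.

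**Excess fully cancelled in the any-MAAE row.** Setting the difference to zero gives x = (1 − b)[1 − (1 − c)/(1 − c(1 − VE))]. With b 30–70%, c 5–20% and VE 30–70%, x runs from 0.5 to 10.4 points, or about 1 to 31 of 300 vaccinees. At b = 50%, c = 10% and VE = 50% it is 0.5 × (1 − 0.90/0.95) = 2.6 points, about 8 infants.

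**Can the non-COVID percentage be recovered from the tables by term?** Not from participant counts, because one infant can have both kinds of event. Suppose 156 of 300 infants have any MAAE and 60 have COVID-19. The number with a non-COVID MAAE is then at least 156 − 60 = 96 and at most 156, that is 32% to 52%.

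**The case against.** Much of the opposing case stands.

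- **Other outputs separate COVID-19 in part.** Tables by system organ class and preferred term show it on its own lines, and listings are planned. Treatment-related rows should largely omit it, because Protocol 8.11.8 classes an event more likely explained by another cause as not related. Protocol Appendix 2 states that COVID-19 itself is not an AESI. A reader might infer that an excess would be hidden from safety review altogether. The documents do not support that: the dilution is confined to aggregate rows, and SAP 6.3 bases safety on clinical review of all parameters. What remains is that participant counts overlap, and that related rows depend on investigator attribution and so drop every event judged unrelated.
- **The primary safety period is short.** SAP 6.1 makes up to 28 days after any vaccination the primary period, and little COVID-19 accrues in it. But the MAAE and SAE endpoints run for the whole study, and the SAP also reports that stage.
- **No decision rule is touched.** A reader might infer a loss of power or a compromised test. Protocol Table 9 plans counts and percentages for MAAEs and SAEs, without confidence intervals or between-arm tests, and the pause rules in Protocol 7.4 do not use aggregate MAAE or SAE percentages.
- **Part 1.** A reader might extend the argument to the 5 µg versus 10 µg comparison. Part 1 has no placebo arm and no hypotheses, so protection cannot mask harm against placebo there. Calendar-time differences between sequential arms affect every seasonal infection, so removing COVID-19 alone would not repair them. SAP section 7 also reports only 18 infants in Arm 2 at the enrolment pause.
- **Home illness visits.** A reader might take Protocol 8.9.3 to exclude cases seen at home. That is doubtful: it also admits cases evaluated by a healthcare provider, and 8.9.3.1 has physicians, advanced practice nurses, physician assistants or registered nurses make the initial assessment. The clearest outlier is 8.9.4, which names only a site visit.

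**Conclusion.** The point holds for Part 2, for the aggregate MAAE and SAE rows, and mainly over the whole study. If the vaccine protects, those rows understate any excess of other events, and the planned participant counts by term cannot restore the missing percentage. The direction follows from the recording rule once there is protection. The size rests wholly on assumed attack rates, protection, background rate and independence. On the inputs above it is about 1 point of an 8-point excess in the 28-day period. Over the whole study it is 2.4 points (10% attack rate, 30% reduction) to 6.8 points (20%, 50%). This is a gap in the planned presentation of a primary safety endpoint, worth closing because it is cheap to close. It is not an error in a test or a stopping rule. The recording rules differ between Protocol sections and must be reconciled, whatever the size of the dilution.

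**What to change.** In SAP 6.3.1.1 and 6.3.1.2, for Part 2 and for both the 28-day and overall stages, keep the all-cause rows. Beside them add MAAE, SAE and severe AE rows that exclude AE records for RT-PCR-confirmed COVID-19, and read the vaccine–placebo comparison from both sets.

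State the rule that links an AE record to a confirmed case, for example a COVID-19 preferred term with a positive RT-PCR within 14 days, repeat cases included. The rule has to be written because SAP 6.5.1.1 covers only first occurrences and the SAP does not tie a case to an AE record.

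Reconcile Protocol 4.1.1.2, 8.9.3, 8.9.3.1, 8.9.4 and 8.11.4 to one recording rule, and say explicitly how a case seen at a home illness visit is recorded.

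Cost: a few extra table rows, one linking rule and aligned wording. No new data collection is needed.
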